14.3. Reporting and Exclusions

14.3.1. Evaluation of Toxicity

All patients will be evaluable for toxicity from the time of their first treatment with cediranib and olaparib.

14.3.2. Evaluation of Response

All patients included in the study must be assessed for response to treatment, even if there are major protocol treatment deviations or if they are ineligible. Each patient will be assigned one of the following categories: 1) complete response, 2) partial response, 3) stable disease, 4) progressive disease, 5) early death from malignant disease, 6) early death from toxicity, 7) early death because of other cause, or 9) unknown (not assessable, insufficient data). By arbitrary convention, category 9 usually designates the "unknown" status of any type of data in a clinical database.

All of the participants who met the eligibility criteria (with the possible exception of those who received no study medication) should be included in the main analysis of the response rate. Participants in response categories 4-9 should be considered to have a treatment failure (disease progression). Thus, an incorrect treatment schedule or drug administration does not result in exclusion from the analysis of the response rate. Precise definitions for categories 4-9, and sometimes category 3, will be protocol specific.

All conclusions should be based on all eligible participants. Subanalyses may then be performed on the basis of a subset of participants, excluding those for whom major protocol deviations have been identified (e.g., early death due to other reasons, early discontinuation of treatment, major protocol violations, etc.). However, these subanalyses may not serve as the basis for drawing conclusions concerning treatment efficacy, and the reasons for excluding participants from the analysis should be clearly reported. The 95% confidence intervals should also be provided.

15. PUBLICATION PLAN

Publication guidelines exist within the DF/HCC Gynecologic Oncology Program. The study principal investigator will be responsible for collection of data, interpretation of data, monitoring of toxicities, and publication of abstracts and final manuscripts. The principal investigator chooses the different authorship slots per the DF/HCC gynecologic oncology program guidelines.

The results will be made public within 24 months of the end of data collection. If a report is planned to be published in a peer-reviewed journal, then that initial release may be an abstract that meets the requirements of the International Committee of Medical Journal Editors. A full report of the outcomes will be made public no later than three (3) years after the end of data collection.

17. APPENDICES

APPENDIX A: Performance Status Criteria

ECOG Performance Status Scale		Karnofsky Performance Scale	
Grade	Description	Percent	Description
0	Normal activity. Fully active, able to carry on all pre-disease performance without restriction.	100	Normal, no complaints, no evidence of disease.
		90	Able to carry on normal activity; minor signs or symptoms of disease.
1	Symptoms, but ambulatory. Restricted in physically strenuous activity, but ambulatory and able to carry out work of a light or sedentary nature (e.g., light housework, office work).	80	Normal activity with effort; some signs or symptoms of disease.
		70	Cares for self, unable to carry on normal activity or to do active work.
2	In bed < 50% of the time. Ambulatory and capable of all self-care, but unable to carry out any work activities. Up and about more than 50% of waking hours.	60	Requires occasional assistance, but is able to care for most of his/her needs.
		50	Requires considerable assistance and frequent medical care.
3	In bed >50% of the time. Capable of only limited self-care, confined to bed or chair more than 50% of waking hours.	40	Disabled, requires special care and assistance.
		30	Severely disabled, hospitalization indicated. Death not imminent.
4	100% bedridden. Completely disabled. Cannot carry on any self-care. Totally confined to bed or chair.	20	Very sick, hospitalization indicated. Death not imminent.
		10	Moribund, fatal processes progressing rapidly.
5	Dead.	0	Dead.

DFCI IRB 09-293 APPENDIX B: PATIENT'S PILL DIARY: CEDIRANIB

Today's Date _____

Patient Name _____ Patient Study ID _____

Cycle # _____
(initials acceptable for patient's name)

INSTRUCTIONS TO THE PATIENT:

1. Complete one form for each cycle (28 days).
2. You will take ___ (number) ___mg (dosage) tablet(s) each morning.
 You may take the tablet(s) one hour before or two hours after eating, as you prefer.
3. Record the date, the number of pills you took, and when you took them.
4. Please bring your pill bottle (including empty bottles) and this form to your physician when you go for your next appointment.

Date	Day	# pills and when taken: cediranib			Comments	Date	Day	# pills and when taken: cediranib			Comments
		15mg	20mg	Time				15mg	20mg	Time	
	1						15				
	2						16				
	3						17				
	4						18				
	5						19				
	6						20				
	7						21				
	8						22				
	9						23				
	10						24				
	11						25				
	12						26				
	13						27				
	14						28				

Patient's Signature: _____ Date: _____

Physician's Office will complete this section:

1. Date patient started protocol treatment _____ Date patient was removed from study _____
2. Patient's planned daily dose _____ Total number of pills taken this month _____

Physician/Nurse/Data Manager's Signature

DFCI IRB 09-293 APPENDIX B: PATIENT'S PILL DIARY: OLAPARIB (CAPSULE)

Today's Date _____

Patient Name _____ Patient Study ID _____

Cycle # _____
(initials acceptable for patient's name)

INSTRUCTIONS TO THE PATIENT:

1. Complete one form for each cycle (28 days).
2. You will take ___ capsules each day twice a day 12 hours apart.
 You must take the capsules on an empty stomach either 1 hour before or 2 hours after meals.
3. Record the date, the number of capsules you took, and when you took them.
4. Please bring your pill bottle (including empty bottles) and this form to your physician when you go for your next appointment.

Date	Day	# capsules and when taken: olaparib				Comments	Date	Day	# capsules and when taken: olaparib				Comments
		#	AM	#	PM				#	AM	#	PM	
	1							15					
	2							16					
	3							17					
	4							18					
	5							19					
	6							20					
	7							21					
	8							22					
	9							23					
	10							24					
	11							25					
	12							26					
	13							27					
	14							28					

Patient's Signature: _____ Date: _____

Physician's Office will complete this section:

1. Date patient started protocol treatment _____ Date patient was removed from study _____
2. Patient's planned daily dose _____ Total number of pills taken this month _____

Physician/Nurse/Data Manager's Signature _____ Date _____

DFCI IRB 09-293 APPENDIX B: PATIENT'S PILL DIARY: PK EXPANSION COHORT

Today's Date _____ Cycle # _____
 Patient Name _____ Patient Study ID _____

1. _____
2. Complete one form for each cycle (28 days).
3. Record the date, the number of tablets you took, and when you took them.
4. Bring your pill bottles (including empty bottles) and this form to every appointment.
5. Do not chew, dissolve, or crush medications. DO NOT make up vomited doses.
6. If you miss a dose, you have up to 2 hours to make this dose up. Otherwise, write "missed" where you would normally write the time of your dose.
7. The first row in the table below is an EXAMPLE ROW for how to complete this diary.

CEDIRANIB Take _____ (number) _____ mg tablets once a day. Take on an empty stomach 1 hour before taking the morning dose of olaparib.					OLAPARIB Take _____ (number) _____ mg and _____ (number) _____ mg tablets twice a day 12 hours apart after a light meal.						
Day	Date	15mg	20mg	AM	Day	Date	25mg	100mg	150mg	AM	PM
1	1/1/15	2	0	7:00	1	1/1/15	2	0	0	8:00	8:00
1					1						
2					2						
3					3						
4					4						
5					5						
6					6						
7					7						
8					8						
9					9						
10					10						
11					11						
12					12						
13					13						
14					14						
15					15						
16					16						
17					17						
18					18						
19					19						
20					20						
21					21						
22					22						
23					23						
24					24						
25					25						
26					26						
27					27						
28					28						

Patient's Signature: _____ Date: _____
 Physician/Nurse/Data Manager's Signature _____ Date _____

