Cediranib has been administered in combination with a number of chemotherapy regimens. Steady-state plasma concentrations of paclitaxel, carboplatin, oxaliplatin, 5-FU (given as mFOLFOX6), docetaxel, pemetrexed, irinotecan, +SN38, gefitinib, or gemcitabine displayed little or no apparent effect (<1.5-fold change) when given in the presence of cediranib. Steady-state PK parameters of cediranib in combination with the chemotherapy agents are comparable to those seen previously with cediranib monotherapy. Additionally, comparison of studies suggests that Western and Japanese patients have similar PK.

Data obtained following a single 45-mg cediranib dose in the presence and absence of a standard high-fat meal showed that food decreases the C_{max} by 33% and AUC by 24%. Cediranib should therefore be administered at least 1 hour before or 2 hours after food.

Safety and Tolerability in Humans

Early clinical data demonstrated that the most common adverse events (AEs) with cediranib included fatigue, diarrhea, nausea, vomiting, hoarseness, hand-foot syndrome, and hypertension.

Hypertension is an expected AE with agents that inhibit VEGF signaling, and is the major cardiovascular AE associated with cediranib treatment. CTC grade 4 hypertension and end-organ damage related to hypertension, such as cerebrovascular events, have been observed with cediranib. Therefore, clinical trials include rigorous monitoring of BP and renal function (creatinine, creatinine clearance, and urinary protein). A hypertension management protocol is incorporated into all clinical study protocols. Patients with pre-existing hypertension may be at particularly high risk of developing moderate or severe hypertension on cediranib and may benefit from having their BP management optimized prior to starting the drug.

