1. Cediranib tablet(s) in the morning on an empty stomach (at least 2 hours after eating)
2. Light meal ~1 hour after taking cediranib
3. Morning olaparib tablet(s) after light meal
4. Evening olaparib tablet(s) 12 hours after morning olaparib dose, taken after a light meal

Phase II

For the Phase 2 portion of this study, patients will be randomized in 1:1 ratio to one of the two following arms:

1. Olaparib 400mg BID (capsule)
2. Cediranib and olaparib at the RP2D (cediranib 30mg daily and olaparib 200mg BID (capsule)) derived from the Phase I portion of this study

Participants enrolled to the Phase II portion of the study will continue treatment with olaparib capsule formulation.

All patients must meet the eligibility criteria for the Phase II portion of the study, as outlined in Section 3. Patient randomization will be stratified based upon:

1. Prior receipt of anti-angiogenic therapy.
2. BRCA mutation status (carrier, non-carrier, unknown).

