8.14. Pharmacokinetic (PK) studies

The steady-state plasma pharmacokinetics of cediranib and olaparib will be defined in a group of 12 patients in the safety expansion cohort treated with the recommended phase II doses of the combination, cediranib 30 mg QD and olaparib 200 mg BID, to assess whether or not the pharmacokinetic behavior of the two drugs is altered by their concurrent administration. Pharmacokinetic sampling will be performed during a single 24 h dosing interval after steady-state pharmacokinetic conditions for the repeated oral dosing schedules have been achieved when each agent is given alone (cycle 0) and again when given together in the same patient (cycle 1). In cycle 0, one group of six patients will receive single agent cediranib p.o. once daily for 7 days and the other group of six patients will receive single agent olaparib p.o. twice daily for 7 days. Pharmacokinetic samples will be collected on day 7 before and for 8 h after the dose is taken in the morning and before dosing on day 8. Combination therapy will begin on day 8 which is formally day 1 of cycle 1. Pharmacokinetic samples will again be collected before and for 8 hr after dosing on days 15-16 after the patients have received 14 days of combined therapy, as per the timepoints outlined below.

The sampling schedule has been devised to accommodate treatment on an outpatient basis. Patients will be instructed to take the doses of the two drugs as per outlined in the protocol at the same time every day during the pharmacokinetic study. Cediranib will be taken first thing in the morning on an empty stomach. One hour later, the patient may have a light meal, followed by the morning dose of olaparib. Dosing should be scheduled for times that will allow the patient to arrive at the clinic to obtain pharmacokinetic samples before dosing and to remain for an additional 8 hours after the morning dose of olaparib. The second daily dose of olaparib should be taken 12.0 ± 0.25 h after the morning dose. It is very important that the patient is aware that the morning doses of the two drugs on day 8 and day 16 must not be taken before arriving at the clinic and the 24.0 h pharmacokinetic sample has been collected. The first set of blood samples (6 mL) will be obtained during cycle 0 shortly before taking the day 7 dose of the single agent drug and at 0.5, 1.0, 2.0, 3.0, 4.0, 6.0, 8.0, and 24.0 h after dosing.

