The second set of blood samples (6 mL) will be obtained during cycle 1 starting on day 15 with the following schedule, to accommodate the sequential dosing schedule of the two drugs:

PK specimen	Day	Timing
#1	Cycle 1 Day 15	Just prior to cediranib dose
#2	Cycle 1 Day 15	0.5 hrs after cediranib dose
#3	Cycle 1 Day 15	1.0 hrs after cediranib dose
#4	Cycle 1 Day 15	2.0 hrs after cediranib dose, just prior to olaparib dose
#5	Cycle 1 Day 15	2.5 hrs after cediranib dose (= 0.5 hrs after olaparib dose)
#6	Cycle 1 Day 15	3.0 hrs after cediranib dose (= 1.0 hrs after olaparib dose)
#7	Cycle 1 Day 15	4.0 hrs after cediranib dose (= 2.0 hrs after olaparib dose)
#8	Cycle 1 Day 15	5.0 hrs after cediranib dose (= 3.0 hrs after olaparib dose)
#9	Cycle 1 Day 15	6.0 hrs after cediranib dose (= 4.0 hrs after olaparib dose)
#10	Cycle 1 Day 15	8.0 hrs after cediranib dose (= 6.0 hrs after olaparib dose)
#11	Cycle 1 Day 16	24.0 hrs after C1D15 cediranib dose, just prior to C1D16 cediranib dose
#12	Cycle 1 Day 16	24.0 hrs after C1D15 morning olaparib dose, just prior to C1D16 morning olaparib dose

Samples will be collected in plastic green stoppered Vacutainer 6.0 mL plasma collection tubes with spray-coated sodium heparin, gently inverted 5-times to thoroughly mix the blood with the anticoagulant, and placed on wet ice until centrifuged (1,300 x g, 10 min, 4°C) within 15 min after collection. Separate the plasma from the blood cells using a disposable pipette and transfer the plasma into a 4.5 mL self-standing polypropylene cryogenic storage vial with external threads (Fisher Scientific, cat. no. 12-565-291). Affix a pre-printed label, with the protocol number, patient accession number, and sample number onto the cryovial, oriented crosswise toward the upper part of the tube, without overlapping the vial cap. Completely cover the label with polyester protective label tape (Fisher Scientific, cat. no. 11-867B) to prevent the label from detaching from the vial when stored frozen. Store the plasma samples in a freezer at <-70°C until packaged for shipment to the analytical laboratory.

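### The PK-cohort diary puts olaparib 1 hour after cediranib but the Cycle 1 Day 15 sampling table assumes 2 hours, so following both either mistimes the olaparib samples or delays the Day 15 olaparib dose by an hour

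*Combined protocol and SAP*

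**What the plan says.** Four places govern the interval between cediranib and the morning olaparib dose in the PK expansion cohorts.

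- **Appendix B, PK Expansion Cohort diary.** Cediranib: "Take on an empty stomach 1 hour before taking the morning dose of olaparib". Olaparib: "tablets twice a day 12 hours apart after a light meal". The example row shows cediranib at 7:00 and olaparib at 8:00 morning and evening.
- **Section 8.14, Cycle 1 table.** Sample #4 on Day 15 is timed as "2.0 hrs after cediranib dose, just prior to olaparib dose". Samples #5 to #10 carry two clocks, one for each drug.
- **Section 5, Phase I-T PK expansion.** The dosing list reads "Light meal ~1 hour after taking cediranib", with the morning olaparib after that meal and no clock time for it.
- **Section 8.14, text.** It gives the same order of cediranib, meal, olaparib, again with no olaparib clock time. Doses are to be taken "at the same time every day during the pharmacokinetic study", and the evening olaparib dose follows the morning one by 12.0 ± 0.25 h.

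On food, Section 2.2.1 says: "Cediranib should therefore be administered at least 1 hour before or 2 hours after food".

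**The concern.** The diary was written for this cohort, so its 1-hour gap cannot be set aside as a generic form. Nothing tells patients or sites to change it on or before Day 15, yet the table that defines the combination-period samples rests on a different gap.

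The PK cohorts exist to show whether either drug's exposure changes when the two are given together. Each patient is compared with herself, alone (Cycle 0) versus combined (Cycle 1), by a paired t-test on log-transformed parameters. The conflict arises only in the combined period, so a timing error there does not cancel in the pairing and could be mistaken for an interaction. Section 8.14 does not say whether the noncompartmental analysis uses nominal or actual times.

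**Working it through.** **Step 1: the table's own gap.** Gap = (hours after cediranib) − (hours after olaparib). For #5 to #10: 2.5 − 0.5, 3 − 1, 4 − 2, 5 − 3, 6 − 4 and 8 − 6, each 2.0 h. Sample #4, just before olaparib at 2.0 h, agrees. The table is internally consistent.

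**Step 2: the diary's gap.** 8:00 − 7:00 = 1 h, matching its instruction. The two differ by 1 h.

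**Step 3, scenario (a): the diary gap is kept on Day 15 and samples are drawn on the cediranib clock.** Time relative to olaparib = hours after cediranib − gap.

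| Sample | h after cediranib | Relative to olaparib, 2 h gap (table) | Relative to olaparib, 1 h gap (diary) |
|---|---|---|---|
| #3 | 1.0 | −1 | 0 |
| #4 | 2.0 | 0 | 1 |
| #5 | 2.5 | 0.5 | 1.5 |
| #6 | 3.0 | 1 | 2 |
| #7 | 4.0 | 2 | 3 |
| #8 | 5.0 | 3 | 4 |
| #9 | 6.0 | 4 | 5 |
| #10 | 8.0 | 6 | 7 |

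The sample labelled as just before olaparib is then 1 h after it. Sample #12 is defined from the olaparib dose itself and is not displaced.

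Cycle 0 samples are pre-dose and at 0.5, 1, 2, 3, 4, 6, 8 and 24 h. With a 2 h gap, Cycle 1 matches all of these for olaparib except 8 h. With a 1 h gap and actual times, #3 serves as pre-dose and the 1, 2, 3, 4 and 24 h points match, while 0.5, 6 and 8 h do not. The contradiction therefore costs the 0.5 h and 6 h matches; the 8 h match is absent under either gap.

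**Step 4, scenario (b): diary on Days 1 to 14, table on Day 15.** Using the diary's example clock, the Day 14 evening dose is at 20:00. With cediranib at 7:00 on Day 15, the table puts olaparib at 9:00. The interval is 4 + 9 = 13 h instead of 12 h. Sample #4 is drawn at 13 h. Sample #3, at 8:00, falls exactly 12 h after the evening dose.

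To give a scale for #4, assume single-exponential decline. The documents state no half-life, so take 4 to 12 h. The level at 13 h relative to 12 h is exp(−ln 2 / half-life), which is 0.84 at 4 h and 0.94 at 12 h: 16% to 6% lower.

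**Step 5: moving cediranib instead.** Keeping olaparib at 8:00 and taking cediranib at 6:00 on Day 15 keeps the olaparib interval, but makes the cediranib interval (24 − 7) + 6 = 23 h.

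**Step 6: food, scenario (a) only.** With olaparib at 1 h and after a light meal, the meal has to fit before the hour is up. That could bring eating inside the interval that Section 2.2.1 asks for between cediranib and food. Under (b), the 2 h gap on the sampled day leaves room for a meal at about 1 h.

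**The case against.** Day 15 sampling takes place in clinic. Sample #4 is defined by an event, and #5 to #10 show olaparib times explicitly, so staff are unlikely to draw a just-before-dose sample an hour after the dose unnoticed. That stands, and it makes (b), a single shifted interval, the more realistic failure.

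Actual times may also be available: patients record dose times in the diary, and a Pharmacokinetic Data Form travels with each sample set. Actual times would correct the labels in (a). But the form's contents are not shown and the analysis text does not commit to using them. Nor can they restore the 0.5 h and 6 h points.

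The method measures both drugs in each sample, so #3 gives a usable olaparib pre-dose level in either scenario. This stands too: the 6% to 16% figure describes #4 alone, not a loss of the trough.

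Three stronger readings are tempting but unsupported:

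- A reader might infer that cediranib exposure would fall by the protocol's figures of 33% for Cmax and 24% for AUC. Those come from a single 45 mg dose with a high-fat meal. Here the meal is light and may be early by only minutes, and under (b) the effect does not follow on the sampled day.
- A reader might infer that the 13 h interval breaches the ±0.25 h tolerance fourfold. That tolerance covers the morning-to-evening interval, and the 13 h runs from evening to morning. What it departs from is the diary's 12-hour spacing and the same-time-every-day instruction.
- A reader might infer that no site can avoid the problem. A site using 2 h every day would avoid it, but only by departing from the diary.

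**Conclusion.** The contradiction is real: 1 h in the cohort's own diary against 2 h in its sampling table, with the dosing text leaving it open. Following both as written gives either a 1 h displacement of #4 to #10 relative to olaparib, with two matched time points lost, or a 13 h interval before the Day 15 olaparib dose. The resulting bias in AUC or Cmax cannot be computed from the documents. A food effect on cediranib is possible under (a) only, and its size is unknown.

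The reach is limited. Olaparib timing affects the six patients who take olaparib alone first; the possible food effect concerns the six who take cediranib alone first. Both comparisons serve a secondary Phase 1-T objective. The MTD and Phase II PFS are untouched. The clock times above assume that the diary's example row is followed. The point merits correction because each comparison is small and paired, and the correction is cheap.

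**What to change.** Reconcile the Section 5 dosing list, the Section 8.14 text, the Cycle 1 table and the PK diary to one cediranib-to-olaparib gap. The choice of gap is the sponsor's. Apply it on every combination day from Cycle 1 Day 1, and re-derive the table's olaparib times from it.

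Add a sentence to Section 8.14 stating that the noncompartmental analysis uses actual times after each drug's recorded dose.

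The cost is wording in the diary, the table and the related text, with no added samples, visits or patients. If patients have already been dosed, reconciliation cannot change their samples, but the actual-time statement still helps.

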APPENDIX D: List of Drugs that May Have Potential CYP3A4 Interactions

CYP3A4 Inducers (prohibited)

Armodafenil ¹	Modafinil ²	Primidone ¹
Barbiturates ²	Nafcillin ¹	Rifabutin
Bosentan ¹	Nevirapine	Rifampin
Carbamazepine	Oxcarbazepine	Rifapentine ¹
Dexamethasone ¹	Pentobarbital ¹	St. John's wort ²
Efavirenz	Phenobarbital	Troglitazone ³
Fosphenytoin ¹	Phenytoin	
Glucocorticoids ² (see note)	Pioglitazone ²	

Note: Topical steroids are permitted. Please contact overall PI if systemic steroids are clinically indicated while on trial.

¹ Cited in Cytochrome P450 Enzymes: Substrates, Inhibitors, and Inducers. In: Lacy CF, Armstrong LL, Goldman MP, Lance LL, eds. Drug Information Handbook 20th ed. Hudson, OH; LexiComp Inc. 2011-2012: 1810-1818

² Cited in Flockhart DA. Drug Interactions: Cytochrome P450 Drug Interaction Table. Indiana University School of Medicine (2007). <http://medicine.iupui.edu/clinpharm/ddis/table.asp>. Accessed Nov 2011.

³ Weak inhibitor per Lacy et al. May be used with caution.

Note: Drugs without a superscript are cited in both the Lacy and Flockhart references.

CYP3A4 Inhibitors

Strong Inhibitors (prohibited)	Moderate Inhibitors (use with caution, avoid if possible)	Weak Inhibitors (use with caution, avoid if possible)
Amprenavir ¹	Amiodarone ¹	Chloramphenicol ²
Atazanavir ¹	Aprepitant	Ciprofloxacin ²
Clarithromycin	Cimetidine ¹	Diethyldithiocarbamate ²
Conivaptan ¹	Clotrimazole ¹	Fluvoxamine ²
Delavirdine ¹	Cyclosporine ¹	Gestodene ²
Fosamprenavir ¹	Desipramine ¹	Mibefradil ²
Fospropofol ¹	Doxycycline ¹	Mifepristone
Imatinib ¹	Efavirenz ¹	Norfluoxetine ²
Indinavir	Erythromycin	Star fruit ²
Isoniazid ¹	Fluconazole	Troleandomycin ²
Itraconazole	Fosaprepitant ¹	
Ketoconazole	Grapefruit juice	
Miconazole ¹	Haloperidol ¹	
Nefazodone	Lidocaine ¹	
Nelfinavir	Metronidazole ¹	
Nicardipine ¹	Norfloxacin ¹	
Posaconazole ¹	Sertraline ¹	
Propofol ¹	Tetracycline ¹	
Quinidine ¹	Verapamil	
Ritonavir	Voriconazole ¹	
Saquinavir ²		
Telithromycin		

¹ Cited in Cytochrome P450 Enzymes: Substrates, Inhibitors, and Inducers. In: Lacy CF, Armstrong LL, Goldman MP, Lance LL, eds. Drug Information Handbook 20th ed. Hudson, OH; LexiComp Inc. 2011-2012: 1810-1818

² Cited in Flockhart DA. Drug Interactions: Cytochrome P450 Drug Interaction Table. Indiana University School of Medicine (2007). <http://medicine.iupui.edu/clinpharm/ddis/table.asp>. Accessed Nov 2011.

Note: Drugs without a superscript are cited in both the Lacy and Flockhart references.

CYP3A4 Substrates (allowed – take note of possible interactions)

Alfentanil	Dexlansoprazole	Isradipine	Ranolazine
Alfuzosin	Dextromethorphan ²	Itraconazole	Refabutin
Alprazolam	Diazepam	Ixabepilone	Repaglinide
Ambrisentan	Dihydroergotamine	Ketamine	Risperidone ²
Amiodarone	Diltiazem	Ketoconazole	Ritonavir
Amlodipine	Disopyramide	Lansoprazole	Salmeterol
Aprepitant	Docetaxel	Lapatinib	Saquinavir
Aripiprazole	Domperidone ²	Lercanidipine ²	Sibutramine
Armodafinil	Doxorubicin	Levonorgestrel	Sildenafil
Astemizole ²	Eletriptan	Lidocaine	Simvastatin
Atazanavir	Efavirenz	Lovastatin ²	Sirolimus
Atorvastatin	Eplerenone	Lopinavir	Solifenacin
Benzphetamine	Ergoloid mesylates	Maraviroc	Spiramycin
Bisoprolol	Ergonovine	Medroxyprogesterone	Sufentanil
Bortezomib	Ergotamine	Mefloquine	Sunitinib
Bosentan	Erlotinib	Mestranol	Tacrolimus
Bromazepam	Erythromycin	Methadone	Tadalafil
Bromocriptine	Escitalopram	Methylgonovine	Tamoxifen
Budesonide	Esomeprazole	Methylprednisolone	Tamsulosin
Buprenorphine	Estradiol	Miconazole	Temsirolimus
Buspirone	Estrogens, conjugated	Midazolam	Telithromycin
Busulfan	synthetic	Mirtazapine	Teniposide
Cafergot ²	Estrogens, conjugated	Modafenil	Terfenadine ²
Caffeine ²	equine	Montelukast	Testosterone ²
Carbamazepine	Estrogens, esterified	Nateglinide	Tetracycline
Cerivastatin ²	Estropipate	Nefazodone	Theophylline
Chlordiazepoxide	Eszopiclone	Nelfinavir	Tiagabine
Chloroquine	Ethinyl estradiol	Nevirapine	Ticlopidine
Chlorpheniramine	Ethosuximide	Nicardipine	Tinidazole
Ciclesonide	Etoposide	Nifedipine	Tipranavir
Cilostazol	Exemestane	Nilotinib	Tolterodine
Cisapride	Felbamate	Nimodipine	Toremifene
Citalopram	Felodipine	Nitrendipine ²	Tramadol
Clarithromycin	Fentanyl	Nisoldipine	Trazodone
Clobazam	Finasteride ²	Norethindrone	Triazolam
Clonazepam	Flunisolide	Norgestrel	Trimethoprim
Clorazepate	Flurazepam	Omeprazole	Trimipramine
Cocaine	Flutamide	Ondansetron	Vardenafil
Codeine ²	Fluticasone	Paclitaxel	Venlafaxine
Colchicine	Fosamprenavir	Paricalcitol	Verapamil
Conivaptan	Fosaprepitant	Pazopanib	Vinblastine
Cyclophosphamide	Gefitinib	Pimozide	Vincristine
Cyclosporine	Haloperidol	Primaquine	Vinorelbine
Dantrolene	Hydrocortisone ²	Propranolol ²	Zaleplon ²
Dapsone	Ifosfamide	Progesterone	Ziprasidone ²
Darifenacin	Imatinib	Quazepam	Zolpidem
Darunavir	Indinavir	Quetiapine	Zonisamide
Dasatinib	Irinotecan	Quinidine	Zopiclone
Delavirdine	Isosorbide dinitrate	Quinine	
Dexamethasone	Isosorbide mononitrate	Rabeprazole	

* Note: CYP3A4 Substrate Table adapted from Cytochrome P450 Enzymes: Substrates, Inhibitors, and Inducers. In: Lacy CF, Armstrong LL, Goldman MP, Lance LL, eds. Drug Information Handbook 20th ed. Hudson, OH; LexiComp Inc. 2011-2012: 1810-1818

** Substrates with ² superscript denote substrates cited in Flockhart DA. Drug Interactions: Cytochrome P450 Drug Interaction Table. Indiana University School of Medicine (2007). <http://medicine.iupui.edu/clinpharm/ddis/table.asp>. Accessed Nov 2011

